15.5 Analysis Plan

A full analysis plan is in development. It is anticipated that the traditional Poisson regression[31] based on cumulative mortality from lung cancer will be performed, as is traditional in screening and prevention trials. It is appreciated that the relative risk estimated from this will be less extreme than might be achieved by repeat screening. We shall therefore additionally analyse the mortality results by fitting the relative hazard of lung cancer mortality as a function of time since randomisation [32] This will improve statistical power and yield estimates which can be compared with those of other screening trials with multiple screen designs.

In addition, we propose to analyse the screening data in terms of detection and interval cancer rates, compliance rates, and false positives rates. In addition to simple descriptive analyses, we shall estimate sensitivity, specificity, and positive and negative predictive values. We shall use Markov process models to estimate lead times [33].

16 Adverse event reporting

16.1 Definitions

ICH GCP defines an Adverse Event as follows:

Adverse Event (AE)

Any untoward medical occurrence in a research participant

Serious Adverse Event (SAE):

Any adverse event, adverse reaction or unexpected adverse reaction, respectively, that:

- results in death
- is life-threatening* (subject at immediate risk of death)
- requires in-patient hospitalisation or prolongation of existing hospitalisation**
- results in persistent or significant disability or incapacity, or
- consists of a congenital anomaly or birth defect
- Other important medical events***

*'Life-threatening' in the definition of 'serious' refers to an event in which the patient was at risk of death at the time of the event; it does not refer to an event which hypothetically might have caused death if it were more severe.

**Hospitalisation is defined as an inpatient admission, regardless of length of stay, even if the hospitalisation is a precautionary measure for continued observation. Hospitalisations for a pre-existing condition, including elective procedures that have not worsened, do not constitute an SAE.

***Other important medical events that may not result in death, be life-threatening, or require hospitalisation may be considered a serious adverse event/experience when, based upon appropriate medical judgment, they may jeopardise the subject and may require medical or surgical intervention to prevent one of the outcomes listed in this definition.

16.2 UKLS Adverse Event Reporting

It is not anticipated that any participant in the UKLS trial will any suffer any adverse events relating to their involvement. Routine adverse events data will not be recorded as part of the participant follow-up. Adverse Events may occur later in the patient pathway if a nodule is discovered and this will be dealt with according to local practice in the treating centre.

17 Ethical Considerations

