5) Overdiagnosis: This is a major issue of any screening trial and can only be assessed in the Main UKLS Trial. The main outcome measure of overall, all-cause mortality will not be influenced by this bias. The pilot will have insufficient power to detect differences in mortality as a result of screening and therefore this bias will only be compensated for in the main trial.

6) Treatments: A significant increase in lung cancer diagnosis and treatment through screening inevitably leads to treatment complications and costs. Lung cancer resection carries a significant complication and mortality rate, influenced by a range of patient characteristics and co-morbidities. A feature of lung cancer surgical treatments is their ongoing capacity to compromise quality of life. Accordingly, the pilot will provide an opportunity to develop and test clinical monitoring forms for all treatments provided to patients with screen-detected cancers – and to examine the associated organisational and training issues.

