6.2 Secondary Endpoint(s)

- To determine the physical morbidity associated with lung cancer screening
- To determine the resource implications of screening and the resulting intervention
- To determine psychosocial consequences of lung cancer screening
- To assess the feasibility of population screening for lung cancer as reflected by uptake of invitations and compliance rates with annual screening
- Establish a blood and tissue bank for the future assessment of early detection diagnostics and novel tumour bio-markers.

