18.4.7 Statistical Monitoring

The recruitment, diagnoses of lung cancer, deaths from lung cancer and adverse events will be regularly reported to the Independent Data and Safety Monitoring Committee (IDSMC). These will be reported separately for each arm of the trial, but with the committee and investigators (apart from the Trials Unit statistician) blinded as to which arm is which. Only in the event of a safety, ethics or efficacy concern on the part of the IDSMC will the arms be identified.

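### Section 16.2 rules out routine adverse event recording, yet a morbidity endpoint and by-arm IDSMC reports depend on such data

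*Protocol*

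**What the plan says.** Section 16.1 of the protocol defines adverse events and serious adverse events. Section 16.2 then opens with the expectation that "It is not anticipated that any participant in the UKLS trial will any suffer any adverse events relating to their involvement", continues with "Routine adverse events data will not be recorded as part of the participant follow-up", and says of events arising once a nodule has been found that "this will be dealt with according to local practice in the treating centre". It gives no trial procedure for collecting or reporting either kind of event.

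Other sections presuppose such data:

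- Section 6.2 lists as the first secondary endpoint of the main trial: "To determine the physical morbidity associated with lung cancer screening". The Protocol Summary (Section 3) has the same item as its first secondary objective.
- Section 18.4.7: "The recruitment, diagnoses of lung cancer, deaths from lung cancer and adverse events will be regularly reported" to the IDSMC, followed by "These will be reported separately for each arm of the trial".
- Section 18.4.2 requires delegated site staff to be trained in SAE reporting.
- Section 21.3 gives the IDSMC interim monitoring of safety.

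The one planned instrument for treatment harms is in Section 4.4.1, where the pilot is to "develop and test clinical monitoring forms for all treatments provided to patients with screen-detected cancers".

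**The concern.** A centre that follows Section 16.2 as written cannot supply what Section 18.4.7 promises, and the morbidity endpoint has no defined source. The gap is widest for people who are investigated and found not to have cancer, since a complication of bronchoscopy, biopsy or resection in them is a harm without a matching benefit. Section 4.4.1 itself accepts that investigation and treatment can cause serious side effects or death, and Section 4.2 rests the choice of a high-risk population on benefit outweighing harm.

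This is more than detail that a statistical analysis plan could supply later. Such a plan cannot analyse data that the protocol says are not routinely collected, and complications not recorded when they occur are hard to recover afterwards.

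**Working it through.** The protocol gives no figure to reproduce here. The check is a comparison of sections, followed by a rough count of the people affected.

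**Which planned source could supply non-fatal physical morbidity?**

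| Source | What it supplies | Work-up complications without cancer? |
|---|---|---|
| Sections 14.1 and 14.2, registry and ONS follow-up | New cancers and deaths | No |
| Section 4.4.1, clinical monitoring forms | Treatment of screen-detected cancers | No |
| Section 3, pilot objective 9 | A database able to hold data on investigations and treatment | Not specified: no complication items, no time window |
| Section 18.4.2, SAE training | Training only | No: Section 16 contains no SAE reporting procedure |
| Section 16.2 | Excludes routine adverse event data; refers to local practice | No |

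None of these supplies adverse events in the control arm either, so a by-arm adverse event report has no source for one of its two columns.

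**How many people are concerned?**

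Inputs:

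- Main-trial scans: 12,800, which is 80% of 16,000 (Section 15.2).
- Share of those screened who have clinical work-up: 1.5%, of whom 70% have lung cancer (Section 4.4.1).
- Pilot screened arm: 2,100 (Section 6.3). Applying the 80% uptake of Section 15.2 to the pilot is my assumption.

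Formulas: worked up = scans × 0.015; without cancer = worked up × (1 − 0.70).

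- Main trial: 12,800 × 0.015 = 192 worked up. With cancer: 192 × 0.70 ≈ 134. Without cancer: 192 × 0.30 ≈ 58.
- Pilot: 2,100 × 0.80 = 1,680 scans; 1,680 × 0.015 ≈ 25 worked up; 25 × 0.30 ≈ 8 without cancer.

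**How large would a wider collection be?**

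Recording complications for every lung cancer in both arms would involve, at the incidence of 0.007 per year in Section 15.2, 32,000 × 0.007 = 224 cancers a year before attrition. Half of these, 16,000 × 0.007 = 112 a year, would be in the control arm, where the trial learns of them through registries.

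**The case against.** Four points can be made for the protocol.

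1. The sentence in Section 16.2 is qualified. It concerns routine data within participant follow-up, and Section 14.1 describes that follow-up as indirect. A reader might infer that all adverse event recording is forbidden. The text does not say so, and it does not prohibit recording complications of an investigation. This stands, but it leaves the by-arm report and the morbidity endpoint without a stated source.

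2. Pilot objective 9 wants the database to hold information on investigations and treatment, with no restriction to confirmed cancers, and Section 15.4 requires clinical data to be uploaded. It would therefore be too strong to say that work-up data are captured nowhere. The accurate statement is that no section provides for recording complications.

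3. A reader might infer that the IDSMC has nothing to monitor, or that the harm side of screening cannot be assessed. The protocol does not support either. Section 18.4.7 also gives the IDSMC lung cancer diagnoses and lung cancer deaths by arm. Total mortality is among the primary endpoints, so a death caused by work-up would count. Section 15.5 plans false positive rates, and Section 14.3 measures cancer worry, anxiety and depression. What lacks a source is non-fatal physical morbidity.

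4. Omitting routine adverse event collection in screened people who need no further work-up is a defensible choice. I accept this, and the remedy below respects it.

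**Conclusion.** The contradiction is in the current text and does not depend on interpretation. Section 16.2 cannot be followed as written while Section 18.4.7 is met and the morbidity endpoint in Section 6.2 is given a source. The specific gap is non-fatal complications of investigation in people without cancer: about 58 of 192 worked up in the main trial, and about 8 of 25 in the pilot.

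These counts rest on the protocol's projections of 1.5% worked up and 70% malignant and on 80% uptake. They also take clinical work-up to be roughly the group referred to the MDT. They scale in proportion if the projections are wrong, and the contradiction does not depend on them.

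It should be fixed, but it is not critical to the trial's main result. It affects a secondary endpoint of the main trial and safety monitoring. The primary mortality comparison and the sample size are untouched.

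**What to change.** Reconcile Sections 16.2, 18.4.7, 6.2, 18.4.2 and 4.4.1, as follows.

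- **Section 16.2:** for every screened-arm participant referred to the MDT, whether or not cancer is confirmed, record on the UKLS database the invasive procedures, their complications, resulting admissions, and deaths within a stated window. Say that these data feed the morbidity endpoint and the IDSMC reports. State the SAE route that site staff are trained in, or remove SAE reporting from the training list in Section 18.4.2.
- **Section 18.4.7:** promise by-arm reporting only of events that are collected in both arms, namely lung cancer diagnoses and deaths. Report work-up complications for the screened arm.
- **Section 4.4.1:** widen the monitoring forms to be tested in the pilot so that they cover work-up as well as treatment, and people without cancer.

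This changes what is recorded and leaves clinical care as it is. The cost is modest data entry at trial centres for about 192 people in the main trial and about 25 in the pilot.

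The drawback is that treatment complications would not be compared with the control arm. Closing that gap would mean following about 224 cancers a year across both arms, with control-arm cases known only through registries. That would be a new collection system rather than an extension of the planned forms, and I do not recommend it as part of this correction.

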17.1 Ethical Considerations

The study will be conducted to conform to the principles of the Declaration of Helsinki as adopted by the 18th World Medical Assembly, 1964 and subsequent amendments (Tokyo (1975), Venice (1983), Hong Kong (1989) and South Africa (1996)). The study will be conducted in compliance with the Medicines (Administration of Radioactive Substances) Regulations 1978 ('MARS') and the principles of Good Clinical Practice.

Patients will be asked to consent that data recorded, collected, stored and processed and may be transferred to other countries, in accordance with any national legislation implementing the EU Data Protection Directive (95/46/EC).

This study may be terminated at the request of the Chief Investigator, IDSMC, or the Independent Ethics Committee if, during the course of the study, concerns about the safety emerge.

17.2 Ethical Approval

Ethical approval will be applied for from the Integrated Research Application System (IRAS). This will include approval from the National Research Ethics Service Committee, NHS R&D, National Information Governance Board for Health and Social Care and Administration of Radioactive Substances Advisory Committee (ARSAC).

All participating sites must undergo site specific assessment (SSA) via IRAS conducted by their local R&D department. A copy of all site approval documentation and a copy of the PIS and ICF on local headed paper should be sent to the LCTU before patients are entered. The LCTU should receive notification of positive SSA and ARSAC for each new centre prior to allowing any patient registration.

After the patient has been registered into the study, the clinician is free to withdraw the patient at any stage if he/she feels it is in the best interest of the patient. However the reason for doing so should be recorded and the patient will remain within the study for the purpose of follow-up and data analysis. Similarly, the patient remains free to withdraw at any time from the protocol and study follow-up without giving reasons and without prejudicing further care.

17.3 Informed Consent Process

Informed consent is a process initiated prior to an individual agreeing to participate in a trial and continues throughout the individual's participation. Informed consent is required for all patients participating in LCTU co-ordinated trials. In obtaining and documenting informed consent, the investigator should comply with applicable regulatory requirements and should adhere to GCP and to the ethical principles that have their origin in the Declaration of Helsinki.

Discussion of objectives, risks and inconveniences of the trial and the conditions under which it is to be conducted are to be provided to participants by staff with experience of taking consent. Participant Information and Consent forms, describing in detail the trial interventions, trial procedures and risks will be approved by an Independent Ethical Committee (IEC) and the participant will be asked to read and

review the document. Upon reviewing the document, the investigator will explain the research study to the patient and their parent/legal representative and answer any questions that may arise. A contact point where further information about the trial may be obtained will be provided.

The patient should have the opportunity to discuss the study and think about it prior to agreeing to participate. After being given adequate time to consider the information (at least 24 hours), the patient will be asked to sign the informed consent document. A copy of the informed consent document will be given to the patient for their records, a copy placed in the medical records, a copy sent to the LCTU for randomisation purposes with the original retained in the Investigator Site File (ISF).

The patient may withdraw from the trial at any time by revoking the informed consent. The rights and welfare of the patients will be protected by emphasising to them that the quality of medical care will not be adversely affected if they decline in this study.

17.4 Data Capture Methods

17.4.1 Radar

Radar is a data capture company that has been selected to manage the UKLS invitation letters and associated questionnaires. Radar have a wealth of knowledge in the field of managing data for large screening projects and have in place clearly outlined data security and disaster recovery policies. Radar is registered and fully compliant under the Data Protection Act.

Radar will take full responsibility for the end to end process for the UKLS project, as outlined in the UKLS Recruitment Pathway (Page 14 – Section 3.0).

Data will be transferred from Radar to UKLS via an external hard drive, encrypted and password protected. Radar are responsible for maintaining security for all data on their equipment and will be automatically backed-up according to Radar's back-up procedure.

Radar will ensure that security is in place on all equipment that data is stored upon.

17.4.2 Questionnaires

The majority of the data collected for the trial will be obtained directly from the participant using lifestyle and psychosocial and Health Economics questionnaires. These questionnaires will form the basis for participant selection. Follow-up questionnaires will also be sent out during the course of the trial to collect further psychosocial data. For the non-screen arm participants will receive a psychosocial questionnaire two weeks after randomisation to the non-screen arm. In the screen arm participants will receive a psychosocial questionnaire two weeks after receiving the result of their baseline scan and any follow up scans required. Data will also be collected during clinic visits. This data will be recorded within patient notes (Source Data) and will be entered onto the UKLS database where necessary.

Timetable of psychosocial measures	Baseline	Follow-up
Demographic and clinical information 
 • Ethnicity • Socioeconomic status / education • Lung screening history (past lung screening; past recall) • Gender* • Age (DOB)* • Smoking – type and frequency* • Family history of lung cancer* 
* Could be accessed from 1st screening risk questionnaire
	✓ ✓ ✓ ✓ ✓ ✓ ✓	x x x x x x x
Cancer distress 6 item Cancer Worry Scale (CWS-R) adapted to lung cancer	✓	✓
General distress Hospital Anxiety and Depression Scale (HADS)	✓	✓
Satisfaction with Decision Scale SWD Scale [34] adapted to decision to take part in lung screening study	✓	✓
Screening expectations & perceptions of CT scan results CARA model [24] Feedback expectancy, i.e. expected CT scan result. To be completed by intervention arm only: perceived feedback threat (“How concerned were you by your CT scan result?” where 1 = not at all concerned, 5 = extremely concerned) and perceived feedback accuracy (“How likely did you think it was that your CT scan result was false or inaccurate?” where 1 = not at all, 5 = a great deal)	✓ x	x ✓
Screening behaviours 
 • Intention to attend further screening • Use of private CT scans 	x x	✓ ✓

Following a Quality Control check and audit of UKLS data captured electronically from the UKLS questionnaires; original copies of the questionnaire will be securely destroyed. Images of every questionnaire will be stored on the UKLS database and affiliated with the relevant participant.

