7. Participants will then complete follow-up psychosocial and health economics questionnaires two weeks after being notified of their CT results, or notification that they are on the control arm of the trial.

Figure 1: UKLS Trial Design

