- Approximately 2 weeks after the clinic visit, participants will be informed to which arm they have been randomised. All smokers will be provided with

smoking cessation advice sheets and a list of local NHS Stop Smoking services.

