8.3 Randomisation

On receipt of the Informed Consent Form, the LCTU utilises the UKLS database management system to randomise individuals. The UKLS database will automatically check eligibility and if eligibility is confirmed will randomise the participant to either the CT screening arm of the trial or the control arm on a 1:1 ratio, using a computer generated random number algorithm. Participants will be notified of their randomised allocation by the LCTU. If the participant has been randomised to the CT arm of the trial the notification letter will include an invitation to have the CT scan and an appointment for the CT scan.

9 Lung cancer Screening

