14.3 Psychosocial and Health Economics

A subset of participants will be asked to take part in the Psychosocial evaluation and Health Economics section of the study. Equal numbers from each study arm will be asked to take part. These participants will be selected at random from the original 4,200 randomised. A brief baseline psychosocial questionnaire will be completed at the clinic recruitment session. Follow-up psychosocial questionnaires will be sent directly to all participants at 1 month post randomisation (i.e. in the screening group, approx. 2 weeks after CT scan results are received – both baseline and follow up scans). These data will be scanned and uploaded onto the UKLS database and analysed.

One objective of the psychosocial evaluation is to assess potential participation bias to the UKLS pilot trial and highlight potential hard to reach groups within this cohort. Analyses will compare the following groups on age, gender and socio-economic status: 1) non-responders, 2) those who complete the non-participation questionnaire (negative responders) and 3) those who complete the UKLS 1st questionnaire (positive responders).

In order to complete these analyses the mail sorting organisation working with UKLS (RADAR) will provide the UKLS study team with data on age and gender of non-responders to the initial approach letter. RADAR will compute the Index of Multiple Deprivation (IMD) scores (a measure of socio-economic deprivation) for all approached individuals using their postcodes and release the IMD information to the UKLS team. The data sent to UKLS is non-identifiable (age, gender and IMD score of each individual).

We have contacted the National Information Governance Board for Health and Social Care (NIGB) who have informed us that we do not need to submit an amendment to them because the proposed analyses are compatible with the purpose of the original NIGB application and there is no flow of patient identifiable information as the UKLS team receive anonymised data from RADAR. Evidence of this can be found within the UKLS Trial Master File.

The Health Economics questionnaire data will be analysed at Nottingham University under the direction of Professor [name].

Psychosocial analysis plan

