The primary psychosocial outcome is cancer worry measured using the 6-item revised Cancer Worry Scale [22, 23] adapted for lung cancer. It is hypothesised that trial participants will report increased short-term cancer worry compared to controls, and that those recalled for further tests will report increased cancer worry in the short- and longer-term.

Preliminary analyses

Attrition analyses will first be conducted to examine the sociodemographic (e.g. gender, age, SES, ethnicity) and clinical (e.g. smoking duration, personal and/or familial experience) factors associated with questionnaire non-response at each stage of the psychosocial assessment, using chi-square and independent t-tests as appropriate. Equivalence of trial/control groups in sociodemographic, clinical, and baseline psychological measures will be examined using chi-square and independent t-tests as appropriate. Descriptive statistics will then be used to characterise study participants in terms of sociodemographic and clinical background factors, and to examine the proportion of the sample reporting clinical levels of HADS anxiety/depression and high levels of cancer-specific worry.

Primary analyses

Prior to the main analysis, multivariate assumptions of normality and linearity will be tested. If the outcome data are reasonably normally distributed, repeated measures analysis of covariance will be used to assess any main effects of trial condition on changes in psychological responses (i.e., cancer worry, anxiety, depression, and decision satisfaction) from baseline to four week follow-up, controlling for potential confounding variables such as gender and baseline distress. If the outcome data are not normally distributed, scores may be transformed to produce a more normal distribution using logarithm transformations.

Secondary analyses

Regression analyses will be carried out to examine the predictors of cancer worry, anxiety, depression, decision satisfaction and screening intention at four weeks. Potential predictors include trial condition/CT screening result, gender, age, SES, ethnicity, smoking duration, personal and/or familial experience of lung cancer, lung screening history, screening expectation, and baseline distress measures.

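### The protocol gives incompatible times for the control-arm psychosocial questionnaire, and its single four-week follow-up does not define when either arm is measured

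*Protocol*

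**What the plan says.** Three sections of the Protocol time the control-arm follow-up questionnaire:

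- **17.4.2 Questionnaires:** "For the non-screen arm participants will receive a psychosocial questionnaire two weeks after randomisation to the non-screen arm".
- **14.3 Psychosocial and Health Economics:** "Follow-up psychosocial questionnaires will be sent directly to all participants at 1 month post randomisation". A parenthesis then equates this, for the screening group, with roughly two weeks after CT results.
- **6.3 UKLS Trial Design, item 7:** follow-up questionnaires are completed "two weeks after being notified of their CT results, or notification that they are on the control arm of the trial".

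Two further sections fix the sequence of events. Section 8.3: "On receipt of the Informed Consent Form, the LCTU utilises the UKLS database management system to randomise individuals". Section 8.2: "Approximately 2 weeks after the clinic visit, participants will be informed to which arm they have been randomised". For the CT arm, the notification letter carries the scan appointment (8.3), the central read takes place within two weeks of the local read (9.4.5), and the questionnaire is tied to the result: "In the screen arm participants will receive a psychosocial questionnaire two weeks after receiving the result of their baseline scan and any follow up scans" (17.4.2).

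The psychosocial analysis plan in 14.3 names cancer worry on the 6-item revised Cancer Worry Scale as its primary outcome and hypothesises a short-term increase against controls. For the primary analysis, "repeated measures analysis of covariance will be used to assess any main effects of trial condition on changes in psychological responses". The sentence goes on to define those changes as running from baseline to a four-week follow-up, with adjustment for gender and baseline distress among other variables. The secondary regressions also refer to outcomes at four weeks.

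**The concern.** A mailing team cannot follow 14.3 and 17.4.2 together, and an analyst cannot tell from 14.3 which questionnaire is the four-week one. The CT arm may return more than one, because follow-up scans trigger further mailings.

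The hypothesis concerns short-term worry, which may change over a few weeks. If one arm is systematically measured earlier than the other, part of any arm difference in worry may reflect time since entry rather than screening. Which arm is earlier, and by how much, depends on which of the three rules is used.

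**Working it through.** The Protocol states no sample size, SD or effect size for this outcome, so there is no planned figure to reproduce. The check is a timeline.

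**Inputs (weeks)**
- Control rules: 2 after randomisation (17.4.2); one month, about 4.3, after randomisation (14.3); 2 after notification (6.3).
- Clinic visit to notification: about 2 (8.2).
- Clinic visit to randomisation: *v*, not stated. Randomisation follows receipt of the consent form (8.3) and comes before notification, so *v* lies between 0 and about 2.
- Notification to scan: *w*, not stated.
- Reading time: *c*, taken as 0 to 2 from the limit on the central read. Any wait for the local read or the result letter would add to it.
- Result to questionnaire, CT arm: 2 (6.3, 17.4.2).

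**Step 1: same anchor.** 4.3 − 2 = 2.3 weeks between 14.3 and 17.4.2. No value of *v* removes this. Against the four-week label in the analysis the gap is 4 − 2 = 2 weeks.

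**Step 2: the third rule.** Under 6.3 a control is measured 2 + 2 = 4 weeks after the clinic visit, which is 4 − *v* after randomisation. With *v* = 0 this is 4 weeks, close to 14.3. With *v* = 2 it is 2 weeks, equal to 17.4.2. So 6.3 can agree with one of the other two sections, never with both.

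**Step 3: the CT arm.** From the clinic visit: 2 + *w* + *c* + 2 = 4 + *w* + *c*. With *c* from 0 to 2:

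| Assumed scan wait *w* | Weeks after clinic visit | After randomisation, *v* = 0 | After randomisation, *v* = 2 |
|---|---|---|---|
| 0 | 4 to 6 | 4 to 6 | 2 to 4 |
| 2 | 6 to 8 | 6 to 8 | 4 to 6 |
| 4 | 8 to 10 | 8 to 10 | 6 to 8 |

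Four weeks is possible, but only for particular combinations of *v*, *w* and *c*. The Protocol fixes none of them.

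**Step 4: gap between arms (CT time minus control time).**

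| Rule used for controls | Formula | *w* = 2, *v* = 0 | *w* = 2, *v* = 2 |
|---|---|---|---|
| 17.4.2 | 2 + *w* + *c* − *v* | 4 to 6 | 2 to 4 |
| 6.3 | *w* + *c* | 2 to 4 | 2 to 4 |
| 14.3 (CT arm timed from result) | *w* + *c* − *v* − 0.3 | 1.7 to 3.7 | −0.3 to 1.7 |

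The two-week scan wait is an assumption used for illustration. The choice between 17.4.2 and 14.3 moves the gap by 2.3 weeks whatever *w*, *c* and *v* are.

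**Step 5: does the analysis wording add a loss of power?** Suppose the arm effect were taken on the average of baseline and follow-up, (y0 + y1)/2, with the same scale's baseline y0 as covariate. Since y0 is in the model, the arm coefficient is exactly half that from the analysis of y1, and so is its standard error; the test is unchanged. In one simulated data set (assumed: 400 per arm, difference 0.2 SD, correlation 0.6) the coefficients were 0.117 for the average and 0.235 for both change and follow-up score, with t = 3.995 in all three.

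**The case against.** **Timing each arm from its own news is a legitimate design.** For short-term worry, equal time since news may matter more than equal time since randomisation. This stands: unequal elapsed time alone is not an error. But only 6.3 states that rule. Section 17.4.2 ties controls to randomisation, and 14.3 claims a common time for everyone, so at least one passage must change on any reading.

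**The month in 14.3 may be a loose description that fits.** If randomisation falls near notification and scan plus reading take about two weeks, the CT arm is measured about four weeks after randomisation. This also stands. A reader might infer that the CT arm is always measured later than four weeks, or that controls are measured just as their allocation letter arrives. Neither can be derived. The first needs a scan wait that is not stated; the second needs both the 17.4.2 rule and randomisation close to the clinic visit.

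**The reference to main effects might be read as diluting the arm difference.** A reader might infer that the repeated-measures model averages in the baseline value and halves the effect, with a large loss of efficiency. The text does not support this. It targets effects on changes from baseline and adjusts for baseline distress, and the table in 17.4.2 lists the Cancer Worry Scale under cancer distress. With that covariate nothing is lost (Step 5). What remains is loose wording: the baseline covariate is not named by scale.

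**It is a minor wording matter.** Psychosocial consequences are a secondary endpoint (6.2), so the weight is limited. Still, the wording decides when questionnaires are mailed for that analysis's primary outcome.

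**Conclusion.** The point holds as an internal inconsistency. Sections 14.3 and 17.4.2 set control-arm times about 2.3 weeks apart from the same anchor, and 6.3 uses a different anchor that can match at most one of them. The four-week follow-up in the analysis does not identify a defined assessment in the CT arm, whose timing depends on unstated scan wait and reading time.

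If 17.4.2 is followed, controls are measured about two weeks earlier than 14.3 and its analysis state, and elapsed time can be confounded with arm for short-term worry. The effect on the worry score cannot be sized, because the Protocol gives no information on how worry changes over those weeks.

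The scope is the psychosocial analysis only. The lung cancer mortality analysis and the sample size in section 15 are unaffected.

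**What to change.** 1. **State one rule in 6.3, 14.3 and 17.4.2.** The simplest is the one in 6.3: two weeks after each arm's own news, meaning the baseline CT result or notification of the control arm. It would replace the randomisation anchor in 17.4.2 and the one-month statement in 14.3. Mailing controls at the CT arm's typical elapsed time is an alternative, but it gives up equal time since news; it is a trade-off, not a requirement.
2. **In the 14.3 analysis plan, replace the four-week label**, in both primary and secondary analyses, with that defined assessment. State that in the CT arm it is the baseline-result questionnaire, not one sent after a follow-up scan.
3. **Report elapsed time from randomisation to questionnaire by arm**, so that any remaining difference is visible. If mailings have already gone out, also report which rule was applied.
4. **Name the covariate:** for cancer worry, the baseline Cancer Worry Scale score.

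The cost is a few sentences of text and, at most, a changed mailing date for a questionnaire already planned. No new data collection is needed beyond recording the dates.
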